### 3.7.2.2 Analyses of Absolute Change

Absolute change in hepatic fat fraction = Week 12 – Baseline.

An analysis will be performed on the absolute change from baseline to Week 12 in hepatic fat fraction by MRI-PDFF. An analysis of covariance (ANCOVA) model with treatment as a factor and baseline value as a covariate will be analyzed. The SAS sample code is listed:

```
*****
** CPDFF = Change in MRI-PDFF from Baseline to Week 12          **
** Trt = Treatment group                                         **
** Base = Baseline value                                         **
*****
PROC GLM data=EFF;
  CLASS Trt;
  MODEL CPDFF = Trt Base;
  LSMEANS Trt / e diff cl;
RUN;
```

In this analysis, the treatment group will be either MGL-3196 active or placebo. A pairwise comparison will be performed between MGL-3196 active and placebo. LS means for the treatment difference, 95% confidence interval and p-value will be provided.

### 3.7.2.3 Week 12 Hepatic Fat Fraction Treatment Goals

There are three treatment goal endpoints that will be used to evaluate the treatment effect.

- % Change from baseline to Week 12 < -30% (% reduction of 30% or more),

- Change from baseline to Week 12  $< -5\%$  (absolute reduction of 5% or more), and
- Week 12 hepatic fat fraction  $< 5\%$ .

For each endpoint, a logistic regression model with treatment as a factor and baseline as a covariate will be used to compare the percentages of patients meeting the following treatment goals between the MGL-3196 versus placebo. The odds ratio, confidence interval, and p-value from the logistic regression will be provided.

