 - o Previous liver biopsy consistent with NASH.

Note: Assessment of the above, or other objective modalities suggested by PI, will occur. The choice of additional procedures, performed during the screening period prior to the screening MRI and liver biopsy, may include calculation of FIB-4, APRI, NAFLD fibrosis scores, and/or performance of fibroscan and/or CAP.

5. Must have confirmation of $\geq 10\%$ liver fat content on MRI-PDFF;

Note: Patients with a liver fat content $>9\%$ but $< 10\%$ on MRI-PDFF and who are highly likely to have NASH as determined by Medical Monitors on biopsy may be included in the study but the total may not exceed 10% of the total study population;

6. Biopsy-proven NASH:

- Must have had prior liver biopsy within 180 days of randomization with fibrosis stage 1 to 3 and a NAS of ≥ 4 with at least a score of 1 in each of the following NAS components:
 - Steatosis (scored 0 to 3),
 - Ballooning degeneration (scored 0 to 2), and
 - Lobular inflammation (scored 0 to 3); and

Note 1: Patients who have clear ballooning with fibrosis but no inflammation or patients who have clear inflammation with fibrosis but no ballooning or patients with clear NASH without fibrosis may be included in the study but the total may not exceed 10% of the total study population;

Note 2: If a historical biopsy is to be used, patients must have had no significant change in metabolic status (diabetes control, lipid metabolism, and/or $>5\%$ weight loss), significant change in diabetes medication, or change in use of medications listed in Exclusion #11 since the biopsy;

Note 3: If a historical biopsy is not available, patients must have confirmation of $\geq 10\%$ liver fat content on MRI-PDFF prior to undergoing liver biopsy. However, if, in the opinion of the patient's physician, the patient would benefit from and be advised to obtain a liver biopsy, the patient may undergo liver biopsy prior to MRI-PDFF;

7. Must have documented historical (3 weeks to 6 months prior to the study entry) ALT and AST levels consistent with the screening ALT and AST values. This consistency is established based on the following:

- If the historical and screening ALT and AST values are both $\leq 1.5 \times$ the upper limit of normal (ULN), there is no limit to the difference between the values

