## 2.3 Study Endpoints

### 2.3.1 Efficacy Variables

#### 2.3.1.1 MRI-PDFF Assessments

The primary efficacy variable is percent change in hepatic fat fraction by MRI-PDFF from baseline at 12 weeks for MGL-3196 80 mg versus placebo in patients with biopsy-proven NASH.

The other related efficacy variables with MRI-PDFF at Week 12 are:

- Change in hepatic fat fraction by MRI-PDFF from baseline;
- Proportion of patients who have 30% or more reduction in hepatic fat fraction by MRI-PDFF from baseline at Week 12, that is, the percent change from baseline to Week 12 is  $\leq -30\%$ ;
- Proportion of patients who have 5% or more absolute reduction in hepatic fat fraction by MRI-PDFF from baseline at Week 12, that is, the change from baseline to Week 12 is  $\leq -5\%$  in hepatic fat; and
- Proportion of patients who have 5% or less hepatic fat fraction by MRI-PDFF at Week 12, that is, the hepatic fat fraction measurement at Week 12 is  $\leq 5\%$ .

The efficacy variables at Week 36 include:

- Five efficacy endpoints in hepatic fat fraction by MRI-PDFF as specified in the primary Week 12 efficacy endpoint from baseline at 36 weeks for MGL-3196 80 mg versus placebo;

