#### 3.7.2.5 Analyses for Week 36 Primary Efficacy Endpoints (MRI-PDFF)

Analyses of hepatic fat fraction from Baseline to Week 36 will follow the same analysis as Week 12, based on the mITT population. This analysis will also be repeated for the 36-Week Per Protocol Population. If there are patients who early withdraw between Weeks 12 and 36, then the following two analyses will be conducted:

- Analyze the primary endpoint (percent or absolute changes in hepatic fat fraction by MRI-PDFF) without the early withdrawals, that is, only include patients who finish Week 36 MRI-PDFF (mITT Population – Observed); and
- Last observation carried forward between Weeks 12 and 36, and use this last observation as the Week 36 value for the analysis (mITT Population – LOCF).

The percent and absolute change in hepatic fat fraction by MRI-PDFF between Week 12 and Week 36 without the early withdrawals will be analyzed, that is, only include patients who finish Week 36 MRI-PDFF. The results between Weeks 12 and 36 will show durability of response and whether MRI-PDFF at week 12 is a good a predictor of response or Week 36 is better.

Additional sensitivity analysis may be performed with other statistical models, such as Mixed effect Model Repeat Measurement (MMRM) method.

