## **4. SAMPLE SIZE DETERMINATION**

Approximately 117 patients in total will be randomized to 80 mg (2/3) or placebo (1/3) treatments. After PK assessment, a significant fraction of patients' combined AUC (MGL-3196 plus MGL-3196-M1) may exceed 5500 ng\*hr/ml resulting in a dose reduction to 60 mg. In order to power the study appropriately for an efficacious dose (which may be  $\geq 80$ mg), randomization may continue until approximately 36 patients have continued at Week 4 on the 80 mg dose. It is estimated that the treatment difference of percent change in hepatic fat fraction from baseline to Week 12 between any dose of MGL-3196 and the placebo group is about -30%. With a common standard deviation for the percent change in hepatic fat fraction at 35%, 36 patients per group completing the Week 12 visit will provide 90% power with a 2-sample t-test. The significance level is set as 0.025 for the consideration of multiplicity in comparisons of 2 daily dosing regimens of MGL-3196 versus the placebo group. The enrollment size is designed to allow for 10% drop out before the Week 12 visit, and as such, patients who drop out of the study will not be replaced.

With the sample size of 39 patients per treatment, the power for selected secondary efficacy endpoints was calculated. The baseline hepatic fat fraction is expected to be approximately 15% to 17%, thus the change from baseline to Week 12 in hepatic fat fraction is approximately -5.5% when comparing to placebo. With common standard deviation of change in hepatic fat fraction as 6%, 36 completed patients will provide 94% power for the study when evaluating the treatment effect in change of hepatic fat fraction.

In addition, the sample size is expected to provide meaningful liver biopsy-related data.

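### The Week 12 goal of fat fraction below 5% has an ordinary logistic model with no named test and no sparse-cell method, though only about one or two placebo events are expected (minor)

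*SAP*

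**What the plan says.** SAP 3.7.2.3 sets three Week 12 goals: a relative fall of 30% or more, an absolute fall of 5 points or more, and a fat fraction below 5%. For each, "a logistic regression model with treatment as a factor and baseline as a covariate will be used to compare the percentages of patients" meeting the goal. On output it says: "The odds ratio, confidence interval, and p-value from the logistic regression will be provided". Unlike SAP 3.7.2.1 and 3.7.2.2, the section gives no sample code. It does not say whether the p-value is Wald, likelihood-ratio, exact or penalised, and it has no rule for an empty cell.

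SAP 2.3.1.1 lists the third goal among the other MRI-PDFF variables, with a slightly different boundary: "Proportion of patients who have 5% or less hepatic fat fraction by MRI-PDFF at Week 12". SAP 3.7.2.5 carries the method forward: "Analyses of hepatic fat fraction from Baseline to Week 36 will follow the same analysis as Week 12".

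The SAP plans Fisher's exact test for biopsy responders (3.7.3). Protocol 10.2.1.2 names that test for categorical secondary variables generally.

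**The concern.** Patients enter with at least 10% liver fat, apart from a capped minority between 9% and 10% (Protocol 4.1, criterion 5). A placebo patient must therefore lose about half of the liver fat, usually more, to get below 5%. If very few do, ordinary logistic regression is in difficulty. With no placebo event, the treatment coefficient runs off to infinity and its standard error grows with it, so a Wald test sees nothing however many treated patients respond. With one or two events the estimate is finite but the Wald test is weak. The table could then show an unusable odds ratio and a large p-value just where the contrast between arms is greatest.

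**Working it through.** **The plan's own power.** SAP section 4 uses 36 v 36, two-sided α 0.025. For percent change the noncentrality is (30/35)·√(36/2) = 3.64 on 70 df, giving 90.8% (stated 90%). For absolute change it is (5.5/6)·√18 = 3.89, giving 94.3% (stated 94%). These inputs reproduce the plan's figures and are used below. The documents give no event rate or power for the 5% goal.

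**Inputs from the documents.**
- Baseline (SAP section 4): "The baseline hepatic fat fraction is expected to be approximately 15% to 17" percent.
- SD of percent change (SAP section 4): "With a common standard deviation for the percent change in hepatic fat fraction at 35" percent.
- Treatment difference (SAP section 4): "between any dose of MGL-3196 and the placebo group is about -30" percent.
- Evaluable patients: 38 placebo and 78 active (Week 12 tables in the Amendment 6 summary of the protocol).

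**Assumptions.** Placebo mean change *m* of 0 to −10%; baseline SD 4–6% above the 10% floor (shifted gamma); normal percent change; two-sided 0.05. The documents give none of these for this goal.

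**Expected placebo events at a fixed baseline *b*.** P = Φ{[100(5 − b)/b − m]/35}, times 38.

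| b | Fall needed | P, m = 0 | × 38 | P, m = −10 | × 38 |
|---|---|---|---|---|---|
| 15% | 66.7% | 2.84% | 1.08 | 5.27% | 2.00 |
| 16% | 68.8% | 2.47% | 0.94 | 4.66% | 1.77 |
| 17% | 70.6% | 2.19% | 0.83 | 4.17% | 1.59 |

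Letting baselines spread above the floor, simulation (600 trials per scenario, Monte Carlo error about 2 points) gives 1.2–2.4 expected placebo events and 12–19 active events.

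**Chance of no placebo event**, over baseline means 15–17% and SD 4–6%: 24–32% at m = 0, 15–20% at m = −5 and 7–12% at m = −10.

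**What the tests do with such tables** (unadjusted):

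| Placebo v active | log OR (SE) | Wald p | Likelihood-ratio p | Fisher p |
|---|---|---|---|---|
| 0/38 v 10/78 | 21.65 (12,890), not a real estimate | 0.999 | 0.004 | 0.029 |
| 1/38 v 10/78 | 1.69 (1.07) | 0.11 | 0.053 | 0.099 |
| 2/38 v 14/78 | 1.37 (0.78) | 0.081 | 0.046 | 0.085 |

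Second row by hand: log OR = ln[(10/68)/(1/37)] = 1.69; SE = √(1/10 + 1/68 + 1/1 + 1/37) = 1.07; z = 1.58.

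**Overall power**, 38 v 78, baseline 16% (SD 5%), active 30 points lower:

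| Test | m = 0 | m = −10 |
|---|---|---|
| Wald | 17% | 56% |
| Fisher's exact | 43% | 60% |
| Firth, penalised likelihood ratio | 54% | 74% |
| Ordinary likelihood ratio | 64% | 73% |

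Separate runs at m = −10 gave 53–56% for Wald and 69–74% for Firth. In trials with no placebo event the Wald test was never significant. With no treatment effect, Firth rejected in about 2.5% of trials and the ordinary likelihood-ratio test in about 7–8%, so part of the latter's apparent power is excess type I error.

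**The other two goals** at m = 0: Φ(−30/35) × 38 = 7.4 and Φ(−5/6) × 38 = 7.7 expected placebo events. These are not sparse in the same way.

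**The case against.** A reader might infer that the SAP, followed as written, would report no difference for 0/38 against 10/78. The text does not support that. It asks for a p-value from a logistic regression and names no test, so a likelihood-ratio p-value would comply equally well, and in that example it is 0.004. Most of the Wald deficit comes from the choice of test rather than from the lack of a penalty. This stands, and it limits the point. It does not remove it: the SAP also promises an odds ratio and interval, and with an empty placebo cell the odds ratio has no finite maximum-likelihood estimate under any test. The ordinary likelihood-ratio test is also liberal here.

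A reader might also take the infinite odds ratio as the expected result. It needs exactly zero placebo events, while one or two are expected. Higher chances of zero arise with a baseline mean of 20%, which is outside the plan's 15–17%.

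The stakes are low. The goal is not primary, SAP 2.1.2 names only the 30% responder goal among its secondary objectives, and the analyses of percent and absolute change use the same scans without this problem. Week 12 data had already been read out: the Amendment 6 tables are dated November 2017 and SAP version 1.0 is dated May 2018. The documents do not show the placebo count for this goal, so nothing here says that the problem occurred.

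Fisher's exact test, already named in the protocol, is a fair alternative for the p-value. It drops the planned baseline adjustment and has less power than Firth in the scenarios above.

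**Conclusion.** The point holds, as a minor one. For the below-5% goal the SAP prescribes a model whose odds ratio has no finite estimate in roughly 7–32% of trials under the plan's baseline and SD, and it leaves open which p-value is reported. If that p-value is Wald, it is near 1 in those trials, and power over all trials is about 17% against 54% for Firth at placebo change 0, or 56% against 74% at −10%. These sizes rest on the assumed placebo mean change, baseline spread and 0.05 level. They also depend on the SD: at 25% instead of 35%, expected placebo events fall to about 0.2 and the chance of none rises to about 82%. The documents give no placebo rate for the Week 36 repeat, so its size is unknown. The conclusion does not extend to the 30% relative and 5-point absolute goals.

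**What to change.** In SAP 3.7.2.3, for the below-5% goal, keep the treatment-plus-baseline model but fit it by Firth's penalised likelihood. Report the penalised likelihood-ratio p-value and a profile-likelihood interval for the odds ratio. Apply the same to the Week 36 repeat in 3.7.2.5. In SAS PROC LOGISTIC this means the FIRTH, CLODDS=PL and CLPARM=PL options, with the penalised likelihood-ratio p-value reported in place of a Wald one. Using the method for the other two goals is optional. Label the Week 12 change as made after the Week 12 readout. In the same edit, reconcile the boundary, which is 5% or less in 2.3.1.1 and below 5% in 3.7.2.3.

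The cost is a few lines of code and text. The downside is that odds ratios shrink slightly towards 1.

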#### 3.7.2.4 Subgroup Analyses for Week 12 Primary Efficacy Endpoints

The analyses of percent change and absolute change in hepatic fat fraction will be performed for the MRI-PDFF Evaluable population for the following subgroups:

- Gender (male, female);
- Weight loss from Screening ( $< 5\%$  weight loss at Week 12,  $\geq 5\%$  weight loss at Week 12);
- Ethnicity (Hispanic or Latino, Not Hispanic or Latino);
- Type 2 diabetes (yes or no);
- PNPLA3 SNP phenotype (homozygous, heterozygous, negative);
- Fibrosis Stage [0-1 (Total), 2-3];
- NAS Score ( $\leq 4$ ,  $> 4$ );
- Week 12 SHBG group ( $\geq 75\%$ ,  $< 75\%$  change from baseline to Week 12);
- Baseline liver fat percentage ( $< 20\%$ ,  $\geq 20\%$ ); and
- Exposure group (AUC  $< 2700$  ng\*hr/mL, AUC  $\geq 2700$  ng\*hr/mL).

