** PCPDFF = Percent change in MRI-PDFF from Baseline to Week 12  **
** Trt = Treatment group                                         **
*****
PROC GLM data=EFF;
  CLASS Trt;
  MODEL PCPDFF = Trt;
  LSMEANS Trt / e diff cl;
RUN;
```

In this analysis, the treatment group will be either MGL-3196 active or placebo. A pairwise comparison will be performed between MGL-3196 active and placebo. LS means for the treatment difference, 95% confidence interval and p-value will be provided.

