- The analyses performed on the NASH Resolutions endpoint will exclude patients with  $>9.5\%$  weight loss from Screening to Week 36 (the percent change in body weight from Screening to Week 36 is  $>-9.5\%$ ), including the patients only as secondary analyses. Conversely, other liver biopsy and study endpoints will include the patients, excluding them only as secondary analyses.

Other liver biopsy variables include:

- The change in fibrosis stage from baseline at 36 weeks; as a continuous variable and descriptively by numbers and percentages of patients in which fibrosis stage improved, was unchanged or worsened, for exploratory purposes only
- The change in portal inflammation from baseline at 36 weeks; and
- The change in parameters of NASH liver biopsy (NAS) from baseline at 36 weeks. The NAS score will also be summarized descriptively as a continuous variable for exploratory purposes only.
- Correlation of reduction of liver fat on MRI-PDFF at 12 and 36 weeks with improvement or resolution of NASH on liver biopsy.

Analyses of liver biopsy data will be performed on the mITT population for the following subgroups:

- Week 36 SHBG group ( $\geq 88\%$ ,  $<88\%$  change from baseline to mean SHBG post Week 12 through Week 36);
- Exposure group (AUC  $<2700$  ng\*hr/mL, AUC  $\geq 2700$  ng\*hr/mL);
- Baseline Fibrosis Stage 2/3;

- Weight loss from Screening to Week 36 (<5% weight loss,  $\geq 5\%$  weight loss,  $< 7\%$  weight loss,  $\geq 7\%$  weight loss,  $> 9.5\%$  weight loss);
- Baseline MRI-PDFF  $\geq 20\%$ ;
- Gender (male, female);
- Ethnicity (Hispanic or Latino, Not Hispanic or Latino );
- Stage of NASH ( $\geq 5$ ,  $< 5$ );
- PNPLA3 SNP phenotype (Homozygous, Heterozygous, negative);
- Type 2 diabetes (yes or no);
- MGL-3196 treated patients who have 30% or more reduction in hepatic fat fraction by MRI-PDFF from baseline at Week 12 and 36, that is, the percent change from baseline to Week 12 and 36 is  $\leq -30\%$  versus all Placebo treated patients;
- MGL-3196 treated patients who have 5% or more absolute reduction in hepatic fat fraction by MRI-PDFF from baseline at Week 36, that is, the change from baseline to Week 12 is  $\leq -5\%$  in hepatic fat versus all Placebo treated patients;
- MGL-3196 treated patients who have 5% or less hepatic fat fraction by MRI-PDFF at Week 12 and 36, that is, the hepatic fat fraction measurement at Week 12 and 36 is  $\leq 5\%$  versus all Placebo treated patients; and

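### Week 12 baseline subgroups get a separate p-value per level and no interaction test, so a uniform effect will probably look different between levels in at least one of the seven factors

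*SAP*

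**What the plan says.** SAP 3.7.2.4 specifies the subgroup work in one sentence: "The analyses of percent change and absolute change in hepatic fat fraction will be performed" in MRI-PDFF Evaluable patients, by subgroup. Ten factors follow. Seven are fixed at baseline: gender, ethnicity, type 2 diabetes, PNPLA3, fibrosis stage, NAS and baseline liver fat. Six of these have two levels; the other is "PNPLA3 SNP phenotype (homozygous, heterozygous, negative"), with three. The remaining three (weight loss at Week 12, Week 12 SHBG change and exposure) are measured after randomisation.

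The analyses being repeated are those of SAP 3.7.2.1, with the statement "MODEL PCPDFF = Trt", and SAP 3.7.2.2, with "MODEL CPDFF = Trt Base". For each, "LS means for the treatment difference, 95% confidence interval and p-value will be provided". Neither model has a subgroup term or an interaction term, and Protocol 10.2.1.4, which says only that subgroup analyses may be done, adds none. The by-exposure tables in the Protocol's Amendment 6 summary show the format in use: one level per table, each with its own p-value against placebo.

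The statements that results are exploratory and not adjusted for multiplicity are in SAP 3.7.3 and 3.7.4, not in 3.7.2.4.

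**The concern.** A subgroup display invites the question whether the drug works differently in, say, men and women. A p-value within each level does not answer it. It tests whether the effect in that level is zero, and it depends on how many patients the level holds. One level can be significant and the other not even when the true effect is identical in both.

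The plan produces exactly these paired p-values and nothing that compares the levels directly. The risk is that a chance pattern in one of seven factors is read as showing who responds.

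**Working it through.** **Inputs.** From SAP section 4: difference of 30 points ("between any dose of MGL-3196 and the placebo group is about -30" percent), SD 35 for percent change; difference 5.5, SD 6 for absolute change; 36 per group, alpha 0.025, power 90%. From the Week 12 tables in the Protocol's Amendment 6 summary: 38 placebo and 78 active patients evaluable. Alpha within each level is taken as two-sided 0.05, inferred from the 95% CIs. Assumed, because the documents do not give them: level prevalences, and independence between factors.

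**Step 1: the plan's own figure.** The standard error is 35 × √(2/36) = 8.25, and 30/8.25 = 3.64. A two-sided t-test at 0.025 on 70 degrees of freedom gives 90.8% power, which agrees with the stated 90%. The stated 94% for absolute change also reproduces (94.3%).

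**Step 2: power within levels, same effect everywhere.** The standard error in a level is 35 × √(1/n_placebo + 1/n_active), with power from the noncentral t. With all 116 patients, power is 99%. The chance that exactly one of two levels is significant is p1(1 − p2) + p2(1 − p1).

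| Split | Placebo/active, larger level | Placebo/active, smaller level | Power, larger | Power, smaller | Exactly one significant |
|---|---|---|---|---|---|
| 50/50 | 19/39 | 19/39 | 85% | 85% | 25% |
| 60/40 | 23/47 | 15/31 | 91% | 76% | 29% |
| 70/30 | 27/55 | 11/23 | 95% | 62% | 39% |

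For example, at 70/30: 0.950 × 0.379 + 0.621 × 0.050 = 0.391. Without rounding patients to whole numbers it is 38%. For absolute change the last column is 19%, 22% and 33%.

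**Step 3: all seven baseline factors together.** Simulation of 3,000 trials per scenario, with a uniform effect, six two-level factors plus three-level PNPLA3, all cut from the same 116 patients, and a t-test in each level.

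| Two-level split; PNPLA3 split | At least one discordant factor, percent change | Same, absolute change |
|---|---|---|
| 50/50; thirds | 77% | 69% |
| 60/40; 30/45/25 | 82% | 78% |
| 70/30; 20/50/30 | 92% | 89% |

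For percent change, the average number of discordant factors runs from 2.3 to 3.1. PNPLA3 alone is discordant in 68% to 74% of trials. Without it, six 50/50 factors give 59% (percent change) and 50% (absolute change). If the uniform effect were 20 points, all seven factors would give about 93%.

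**Step 4: correlated factors.** With seven two-level factors, the smaller level holding 35% to 50%, and a 30-point effect, 67% of trials had at least one discordant factor under independence. With latent correlation of 0.3 to 0.5 the result was 64% to 69%.

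**Step 5: the like-for-like comparator.** One interaction test per factor at 0.05 gives a false signal in 5% of tests by construction. Across seven independent tests, 1 − 0.95⁷ = 30%; the simulation gave 29% to 31%.

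**Step 6: power of the interaction test.** At a 50/50 split the within-level standard error is 35 × √(1/19 + 1/39) = 9.79, so that of the difference between levels is √2 × 9.79, about 13.8 points. Power is about 57% for a 30-point difference in effect and about 19% for a 15-point difference.

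**The case against.** The strongest reply is that the SAP never says it will compare significance between levels. It supplies CIs, states no purpose for the baseline subgroups, and the harm needs a reader to misuse the tables. That is fair on intent, and the primary comparison is untouched. But a plan that prints a p-value in every level and no comparison between levels offers a reader nothing else from which to judge a difference. An exploratory label would not change that: multiplicity is one issue, and testing the wrong contrast is another.

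The second reply is that the remedy is weak, and this stands. Unadjusted interaction tests still give a false signal somewhere in about 30% of trials, and they miss moderate real differences. The estimate and CI should therefore lead.

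Four stronger readings are tempting and are not supported:

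- A reader might infer that any given factor will usually look discordant. For a two-level factor at the design effect the chance is about 25% to 39%; only the set of seven makes it likely.
- A reader might blame unequal level sizes. At 50/50 the powers are equal and discordance is still 25%, so limited power plus chance is the main cause and imbalance adds to it.
- A reader might set 77% to 92% against 5%. The first is for at least one of seven factors and the second is for one test; the fair comparator is 30%.
- A reader might extend the same term to SAP 3.7.3, where "Analyses of liver biopsy data will be performed on the mITT population for the following subgroups". The responder endpoints there use Fisher's exact test, which has no interaction term. Baseline fibrosis and baseline liver fat are each listed there with only one level.

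**Conclusion.** The point holds for the seven Week 12 baseline factors in SAP 3.7.2.4. The planned output tests each level against zero effect and never tests whether levels differ. Under a uniform effect of the design size, at least one factor shows a misleading pattern in about 77% to 92% of trials for percent change and 69% to 89% for absolute change, against about 30% with one interaction test per factor.

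These sizes rest on assumed splits up to 70/30, independent factors, normal outcomes and 38 v 78 evaluable patients. The sensitivity check suggests that moderate correlation changes the figure little. That no interaction test is planned rests on its absence from both documents. The weight-loss, SHBG and exposure groups form after randomisation; they are a separate problem that an interaction term would not repair.

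**What to change.** Amend SAP 3.7.2.4 as follows for the seven baseline factors:

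- Fit one model per factor with treatment, factor and treatment-by-factor interaction, plus baseline value for absolute change. For PNPLA3 the interaction test has two degrees of freedom.
- Report the interaction estimate, 95% CI and p-value. Show within-level effects with CIs.
- State that any claim of a differing effect rests on the interaction and not on within-level p-values.
- Label the results exploratory, and say that interaction power is low (about 57% for a 30-point and 19% for a 15-point difference at a 50/50 split) and that seven unadjusted tests carry about a 30% chance of at least one false signal.

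The cost is two added terms per model (factor and interaction), with no new data and no change to the primary analysis. If the biopsy subgroups in SAP 3.7.3 are to support statements about differing effects, they need a separate model, for example logistic regression with provision for sparse cells, and both levels of every baseline factor. That is a larger change and should be decided separately.
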